Eligibility criteria	 Study population: All individuals eligible to be vaccinated. Enrollment period: From the start of the SARS-CoV-2 vaccination campaign (January 1, 2021) to the start of the SARS-CoV-2 booster vaccination campaign (September 1, 2021). Age: 5 to 115 years old, included (all individuals eligible to be vaccinated). Previous infection: Individuals without a SARS-CoV-2 infection before enrolment. Country: Individuals living in the respective country 	 Study population: All individuals vaccinated with at least one dose of the SARS-CoV-2 vaccine (any of the available brands) and all individuals eligible to be vaccinated with a documented positive diagnosis (irrespective of the type of test) for SARS-CoV-2 infection during the data extraction period. Enrollment period: From the start of the SARS-CoV-2 vaccination campaign (January 1, 2021) until the start of the SARS-CoV-2 booster vaccination campaign (September 1, 2021). Age: 5 to 115 years old, included (all individuals eligible to be vaccinated). Previous infection: Individuals without a documented confirmed infection before completing the primary vaccination schedule (i.e. enrolment) or before January 1, 2021 (SARS-CoV-2 vaccine roll-out) for those not having completed a primary vaccination schedule (controls). Country: Resident of the registered individuals in the COVID-19 cases and vaccination datasets. Individuals with neither a registered vaccine dose nor a positive diagnosis during the data extraction period are therefore excluded.
Treatment strategies	 Primary analysis Completing a primary vaccination schedule (from any vaccine brand) Not completing a primary vaccination schedule (either not receiving a vaccine or being only partially vaccinated). Secondary analysis Completing a homogeneous primary vaccination schedule with 	Same as in Target Trial Specification. Vaccination status ascertainment (including brand, dose and date) based on the vaccination registry. Date of being primary vaccinated (completing a primary vaccination schedule) is considered as 14 days after receiving the final dose of the primary vaccination schedule (one dose for the Johnson-Johnson vaccine and two doses of any of the other vaccines considered).

Table 1. Protocol of the target randomised control trial and target trial emulation by using observational data.

Funded by

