BY-COVID is funded by the European Union's Horizon Europe research the European Union and innovation programme under grant agreement number 101046203.

4

Funded by the European Union

	a specific brand (BioNTech-Pfizer, Moderna, Johnson-Johnson, Astrazeneca, Novavax) 2) Not completing a primary vaccination schedule (either not receiving a vaccine or being only partially vaccinated). Pragmatic trial: strategies compared under the usual conditions.	
Assignment procedures	Participants will be randomly assigned, at baseline, to either completing the primary vaccination schedule or to not completing the primary vaccination schedule (no or only partial vaccination). The participants will be aware of the strategy to which they have been assigned (i.e., without blind assignment).	To mimic randomization, we need to adjust for all confounding factors required to ensure comparability (conditional exchangeability) of the groups defined by vaccination (as identified in the Directed Acyclic Graph (13)). We assume that individuals are randomly assigned within levels of baseline covariates: Age, Gender, Comorbidities, ImmuneStatus, EssentialWorker, Foreign, Institutionalised people, Pregnancy, and ResidenceArea. The adjustment will be performed via matching.

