Randomization is mimicked by matching on all confounding factors required to ensure comparability (conditional exchangeability) of the groups defined by vaccination (as identified in the Directed Acyclic Graph, see causal model specification published in Zenodo (13)). For each day during the enrollment period (i.e., sequential emulated trial), all newly vaccinated individuals (i.e. those having completed the primary vaccination schedule) will be matched in a 1:1 ratio to unvaccinated (or partially vaccinated) controls based on the variables listed in the adjustment set to close non-causal backdoor paths and so, eliminate confounding bias (16): age, gender, residence area, pregnancy, being an essential worker, being institutionalised, being a foreigner, presence of comorbidities, and the immune status. Presence of comorbidities is defined as having one of the following conditions: diabetes, obesity, health failure, COPD, a solid tumour without metastasis, chronic kidney disease, sickle cell disease, chronic liver disease, and hypertension (see the data model specification published in Zenodo (13) for variable-level specification, including data dictionaries and crosswalks defining each variable using several international disease *classification systems*). Immune status is defined as having one of the following conditions: HIV infection. blood cancer, transplantation, primary immunodeficiency, immunosuppression (see the data model specification published in Zenodo (13) for variable-level specification and crosswalks).

The matching will be performed using exact matching (whenever possible) or distance based algorithms such as nearest neighbour matching based on the Mahalanobis distance based on the probability of intervention (vaccination) for those individuals not matched using exact matching. Covariate balance after matching will be evaluated considering mean differences between variable values (standardised for continuous variables) between vaccinated and unvaccinated groups, with a difference of 0.1 or less considered to be acceptable.

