For each person, follow-up ends at the occurrence of the outcome event (i.e., a confirmed SARS-CoV-2 infection), death (all causes), completing primary vaccination (for unvaccinated or partially vaccinated controls), completing primary vaccination of the matched control (for vaccinated persons), vaccination with a booster dose (for vaccinated persons), vaccination with a booster dose of the matched vaccinated person (for unvaccinated or partially vaccinated controls), or the end of the study period (i.e., the most

BY-COVID is funded by the European Union's Horizon Europe research the European Union and innovation programme under grant agreement number 101046203.

recent date at which data is available at time of analysis). Newly vaccinated persons (completing a primary vaccination schedule) are eligible for inclusion in the study, even if they have previously been selected as a control. As such, the matched controls enrolled at a particular day during the enrollment period are those who are unvaccinated (or partially vaccinated) at this date but may receive a first (or second) vaccination dose at a later date during the data extraction period.

Differences in the occurrence of a SARS-CoV-2 infection (as a time-to-event outcome) between primary vaccinated and unvaccinated or partially vaccinated individuals (average treatment effect, ATE (16)) will be computed by using adjusted Cox proportional-hazards models (17), and hazard ratios (HRs) and a robust variance estimate will be obtained.

A secondary analysis will be performed where the effectiveness of primary vaccination in preventing SARS-CoV-2 infection is assessed for different vaccine brands (e.g. BioNTech-Pfizer, Moderna, Johnson-Johnson, Astrazeneca, Novavax), hence conducting a stratified analysis using the matched pairs constructed for the primary analysis. Further, we can assess vaccine effectiveness during different time periods, with a dominant circulation of different SARS-CoV-2 variants.

Several sensitivity analyses will be performed accounting for different imputation algorithms, and different matching algorithms and compared in covariate balance after matching, robustness of the survival estimate and computing efficiency of the algorithm.

HRs and variance estimates will be collected from each country or region, and a meta-analysis will be performed in which the HRs are pooled by using the inverse variance method (18).

Ethical aspects

Balance risk/benefit

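### Brand-specific hazard ratios average over each brand's own completion dates and follow-up, and balance is checked only overall, so the stated analysis does not separate brand from timing

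*Protocol*

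**What the plan says.** **Brand contrast.** In Table 1 of the Protocol (Treatment strategies, secondary analysis) the treated strategy is "Completing a homogeneous primary vaccination schedule with" one named brand; five brands are listed. The comparator is no or only partial primary vaccination. No contrast of one brand with another is defined.

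**How it is estimated.** The Statistical analysis plan section does this by "hence conducting a stratified analysis using the matched pairs constructed for the primary analysis". The model is an adjusted Cox regression with robust variance. No term for calendar time or time since completion is named, so as written each brand receives one HR for the whole period. The same section says that effectiveness can also be assessed in periods dominated by different variants. That is worded as optional and is not crossed with brand.

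**Matching.** On each enrolment day the newly vaccinated "will be matched in a 1:1 ratio to unvaccinated (or partially vaccinated) controls based on the variables listed in the adjustment set". On method: "The matching will be performed using exact matching (whenever possible) or distance based algorithms".

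**Balance.** "Covariate balance after matching will be evaluated considering mean differences between variable values", the comparison being "between vaccinated and unvaccinated groups, with a difference of 0.1 or less considered to be acceptable". Brand is not mentioned.

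**Follow-up.** The target trial column of Table 1 stops at 168 days. The emulation column and the Statistical analysis plan section carry no such limit: follow-up can run to the latest data available, unless infection, death, a booster or the control's completed vaccination ends it first.

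**The concern.** An HR fitted over a whole period is an average of the day-by-day HRs, weighted by where the infections fall. Splitting the primary pairs by brand leaves each brand with its own weights: its own completion dates, its own position relative to variant changes, and its own length of follow-up. If effectiveness is not constant, two products with the same effectiveness at every moment can return different HRs. The protocol's interest in variant periods shows that it allows for effectiveness varying over time.

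The second issue concerns each brand's own estimate. A balance limit met by all pairs together need not be met in a subset. Imbalance from distance-matched pairs may be concentrated in one brand, or may run in opposite directions in two brands and cancel.

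At stake is how the brand results are read. HRs for several brands, from a study that aims to inform vaccine policy, will be compared by readers, and the protocol gives no caution against doing so.

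**Working it through.** The Protocol states no sample size, event count or brand-specific figure, so there is nothing to reproduce. Three checks follow.

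**1. Possible follow-up.** Enrolment runs from 1 January to 1 September 2021, which is 243 days. The emulation's end date is open; the target trial's 1 March 2022 is assumed here.
- Completion on 1 January 2021: up to 424 days.
- Completion on 1 September 2021: up to 424 − 243 = 181 days.

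**2. Identical brands with different completion windows.** All inputs other than the dates are assumptions for illustration:
- completion on days 0–90 (early) or days 153–243 (late), counted from 1 January 2021;
- control hazard 0.0003 per day, stepping up to 0.003 per day at day 349;
- pair censoring of 0.001, 0.005 or 0.015 per day;
- data end at day 424.

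For each window the expected Cox score equation was solved for b, the HR:

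Σ over days t since baseline of [d₁(t) − (d₁(t) + d₀(t)) · b·Y₁(t) / (Y₀(t) + b·Y₁(t))] = 0,

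where Y₁ and Y₀ are the expected numbers at risk, and d₁ and d₀ the expected infections, in vaccinated and controls.

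| True HR, same for both brands | Censoring/day | HR early | HR late | Late minus early |
|---|---|---|---|---|
| Constant 0.20 | all three | 0.20 | 0.20 | 0 |
| 0.20, then 0.50 from day 349 | 0.001 | 0.396 | 0.443 | +0.047 |
| | 0.005 | 0.335 | 0.418 | +0.083 |
| | 0.015 | 0.220 | 0.333 | +0.113 |
| 0.20, then 0.80 from day 349 | 0.001 | 0.587 | 0.680 | +0.093 |
| | 0.005 | 0.465 | 0.631 | +0.166 |
| | 0.015 | 0.239 | 0.462 | +0.223 |
| Waning, 0.20 to 0.60 over 240 days | 0.001 | 0.540 | 0.475 | −0.065 |
| | 0.005 | 0.480 | 0.451 | −0.029 |
| | 0.015 | 0.322 | 0.372 | +0.050 |

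Effectiveness is 1 − HR, so the gaps run from about 3 to about 22 effectiveness points, and the sign changes under waning. A 168-day limit alone does not remove them: in the 0.20-to-0.50 case the early window then gives 0.20 and the late window 0.37, 0.35 and 0.28 at the three censoring rates.

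**3. Balance within a brand.** The overall mean difference is D = Σ p_b·d_b, where p_b is a brand's share of pairs and d_b its own difference (for standardised differences, taking a common standard deviation). If D = 0.1 and all other brands have d = 0, then d_b = 0.1 / p_b:
- share 25%: 0.1 / 0.25 = 0.4;
- share 10%: 0.1 / 0.10 = 1.0.

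Two brands with equal shares and differences of +0.2 and −0.2 give D = 0. These are limits, not predictions. An exact pair contributes a difference of zero, so for a yes/no covariate d_b cannot exceed the share of that brand's pairs that are not exact; reaching 0.4 would need at least 40% of them to be distance-matched.

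**The case against.** The strongest reply is that the protocol plans no brand-against-brand comparison. Each brand is set against non-completion, each vaccinated person has a control from the same day matched on nine characteristics, and splitting by the vaccinated member's brand keeps pairs whole. An HR averaged over a brand's own recipients and dates is a legitimate effect among those treated. This stands. A reader might infer that the brand HRs are confounded by calendar time; the documents do not support that, and the constant-HR case above shows that splitting by itself creates no gap.

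The premise is also assumed. The Protocol gives no roll-out dates or recipient profiles by brand, so different windows are not shown by the document, and the sizes above depend on chosen inputs. This stands too: the claim is that identical brands could differ, not that they will.

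A reader might go further and say that brand and timing cannot be told apart. That is too strong. Brand and vaccination date are recorded, so they can be separated where brands overlap in time; the stated analysis simply does not do so. Nor does the Protocol promise a table of brand HRs for policy use: the policy aim belongs to the study as a whole.

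On balance, the Protocol is silent on subgroups rather than restricting the check; exact pairs stay balanced in any subset; the Cox model is described as adjusted; and sensitivity analyses will compare matching algorithms on balance. A brand-level check might also sit in a separate analysis plan that is not at hand. These points narrow the concern to distance-matched pairs, whose share is unknown. They do not remove it, because the only stated limit is the overall one and the adjustment terms within brand are not named.

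**Conclusion.** The point holds in a limited form. Each brand's HR against non-completion is a valid target, protected by same-day matching. Read side by side, whole-period brand HRs mix brand with completion date and length of follow-up, and the stated analysis does not separate them. Under the assumptions shown, identical brands differ by about 3 to 22 effectiveness points in either direction. This requires both that effectiveness varies by variant or time since completion and that brands were completed at different times; without the first there is no gap. The 0.1 balance limit also does not guarantee balance within a brand where distance-matched pairs are used. This is a worthwhile, inexpensive improvement to a secondary analysis. It does not affect the primary result.

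**What to change.** Amend the brand paragraph of the Statistical analysis plan section:

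- **Balance.** Apply the existing 0.1 check within each brand stratum. Where it fails, rematch within that brand or restrict that brand's analysis to exactly matched pairs.
- **Timing.** Report brand HRs by interval since baseline and by calendar or variant period, crossing the period analysis already foreseen with brand.
- **Interpretation.** State that each whole-period brand HR is a contrast with non-completion and that these HRs are not to be ranked against one another.

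The cost is protocol wording and extra pipeline output at each site, with no new data. Estimates by brand and period will be less precise, and some cells will be empty for rarely used brands. Restricting to exact pairs also loses pairs. A full brand-against-brand comparison reweighted to common dates and recipients would be a new question and is not needed here.

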Annex I - Supporting documentation

A causal model (DAG), a common data model specification and a simulated dataset following the specifications of the common data model are available at https://doi.org/10.5281/zenodo.6913046

Funded by the European Union

Funded by the European Union

BY-COVID is funded by the European Union's Horizon Europe research and innovation programme under grant agreement number 101046203.
